## **9.4. Values of Potential Clinical Importance**

### **9.4.1. Laboratory Parameters**

Reference ranges for all laboratory parameters collected throughout the study are provided by the laboratory. A laboratory value that is outside the reference range is considered either high abnormal (value above the upper limit of the reference range) or low abnormal (value below the lower limit of the reference range). Note: a high abnormal or low abnormal laboratory value is not necessarily of clinical concern. The laboratory reference ranges will be provided on the listings of laboratory data. Clinical laboratory test results outside of the reference range will be flagged in the listings.

To identify laboratory values of potential clinical importance, National Cancer Institute Common Terminology Criteria for Adverse Events (NCI-CTCAE v4.0) will be used to assign grades to the relevant laboratory parameters. NCI-CTCAE v4.0 can be found at <http://ctep.cancer.gov/reporting/ctc.html>.

For laboratory data which are not listed in the NCI CTCAE v4.0, a summary of values outside the normal range will be provided.

### **9.4.2. ECG Parameters:**

The following criteria will be used to flag electrocardiogram (ECG) values that are values of potential clinical importance:

To identify QTc (Bazett's) values of potential clinical importance, NCI-CTCAE v4.0 will be used to assign grades (see adverse event 'Electrocardiogram QT corrected interval prolonged'). Note that there is a slight inconsistency between CTCAE v4 and ICH E14 (Absolute QTc interval prolongation). It was decided to align with CTCAE for the oncology standard categories.

ECG Parameter	Potential Clinical Importance (PCI) Range	Unit
Absolute QTcB interval	≥450 to <481 (Grade 1) ≥481 to <501 (Grade 2) ≥501 (Grade 3)	Msec
Increase from baseline QTcB	Increase of ≥31 to ≤60 Increase of >60	Msec

The following criteria will be used to flag other ECG values that are values of potential clinical importance:

ECG Parameter	Potential Clinical Importance (PCI) Range	Unit
PR interval	<110 (L) and >220 (H)	Msec
QRS interval	<75 (L) and >110 (H)	Msec

### 9.4.3. Vital Signs

To identify heart rate values of potential clinical importance, NCI-CTCAE v4.0 will be used to assign categories that align with the grades for ‘Sinus bradycardia’, ‘Sinus tachycardia’, ‘Supraventricular tachycardia’, and ‘Ventricular tachycardia’.

The following criteria will be used to flag vital sign values that are values of potential clinical importance:

Vital Sign Parameter	Potential Clinical Importance (PCI) Range	Unit
Decrease from baseline Heart Rate	Decrease to <60	bpm
Increase from baseline Heart Rate	Increase to >100	bpm

To identify blood pressure values of potential clinical importance, NCI-CTCAE v4.0 will be used to assign categories that align with the grades for ‘Hypertension’.

Vital Sign Parameter	Potential Clinical Importance (PCI) Range	Unit
Increase from baseline Systolic Blood Pressure	≥120 to <140 (Grade 1) ≥140 to <160 (Grade 2) ≥160 (Grade 3)	mmHg
Increase from baseline Diastolic Blood Pressure	≥80 to <90 (Grade 1) ≥90 to <100 (Grade 2) ≥100 (Grade 3)	mmHg

To identify temperature values of potential clinical importance, NCI-CTCAE v4.0 will be used to assign categories that align with the grades for ‘Hypothermia’ and ‘Fever’.

Vital Sign Parameter	Potential Clinical Importance (PCI) Range	Unit
Increase from baseline temperature	Increase to ≥38	Degrees C
Decrease from baseline Diastolic Blood Pressure	Decrease to ≤35	Degrees C

#### 9.4.4. Left Ventricular Ejection Fraction

The following criteria will be used to flag left ventricular ejection fraction (LVEF) values that are values of potential clinical importance:

To identify LVEF values of potential clinical importance, NCI-CTCAE v4.0 will be used to assign categories that align with the grades for ‘Ejection fraction decreased’.

LVEF Parameter	Potential Clinical Importance (PCI) Range	Unit
Absolute change from baseline LVEF	
 
• No change or any increase
 
• Any decrease 
 
○ >0-<10 decrease
 
○ 10-19 decrease
 
○ ≥20 decrease
 
○ ≥10 decrease and ≥ LLN
 
○ ≥10 decrease and below LLN
 
○ >10 decrease and below LLN
 
○ ≥20 decrease and ≥ LLN
 
○ ≥20 decrease and below LLN
 
 
 
	%
Relative change from baseline LVEF	
 
• ≥20 decrease and ≥ LLN
 
• ≥20 decrease and below LLN
 
	%

## 10. STUDY POPULATION

Unless otherwise stated, all tables and listings in this section will be based on the All Treated Subjects population, and all summaries and data listings will use treatment labels as specified in Section 7.

The list of displays for Study Population, including the population to use for each display, is shown in Section 14 of the RAP.

### 10.1. Disposition of Subjects

A summary of the number of subjects in each of the analysis populations described in Section 6 will be provided. In addition, the number of subjects enrolled will be summarized for All Treated Subjects population. Subjects in the All Enrolled population who are not in the All Treated Subjects population will be listed.

A summary of subject status and reason for study withdrawal will be provided. This display will show the number and percentage of subjects who withdrew from the study, including primary reasons for study withdrawal. Reasons for study withdrawal will be presented in the order they are displayed in the eCRF.

A summary of study treatment status will be provided. This display will show the number and percentage of subjects who have completed the study, are ongoing, or have discontinued study treatment and a summary of the primary reasons for discontinuation of study treatment. Reasons for study treatment discontinuation will be presented in the order they are displayed in the eCRF. A listing of study treatment discontinuation will be generated. The listing will include last dose date, and reasons for study treatment discontinuation.

### 10.2. Protocol Deviations

All the protocol deviations will be summarized and list the important protocol deviations and will include inclusion/exclusion deviations as well as other deviations.

A separate summary and listing of inclusion/exclusion deviations will also be provided.

### 10.3. Demographic and Baseline Characteristics

The demographic characteristics (e.g., age, race, ethnicity, sex, baseline height, and baseline body weight) will be summarized and listed. Age, height and weight will be summarized using the mean, standard deviation, minimum, median, and maximum. In addition, age will also be categorized and summarized by <18, 18-64, 65-74, and >74. The count and percentage will be computed for sex and ethnicity.

Race and racial combinations will be summarized and listed.

Disease history and characteristics (time since initial diagnosis in months, stage at initial diagnosis, date of initial diagnosis) at initial diagnosis and screening will be listed. Separate summaries of disease characteristics at initial diagnosis and screening will be

provided. Medical conditions present at screening will be listed and will be summarized by past and current cancer-related categories.

A summary of extracranial disease burden at baseline will be produced.

Substance use, including smoking history and alcohol use, will be summarized and listed.

Prior anti-cancer therapy will be coded using WHODrug coding dictionary, then summarized by cohort and listed. A listing of prior anti-cancer therapy will show the relationship between ATC Level 1, Ingredient, and verbatim text. A summary of the number of prior anti-cancer therapy regimens will also be produced.

Prior anti-cancer radiotherapy will be summarized and listed. Prior cancer-related surgeries will be summarized and listed.

#### **10.4. Treatment Compliance**

A listing of planned and actual treatments will be produced.

A listing of drug accountability data (dispensed and returned) will be produced.

A summary of overall compliance for dabrafenib and trametinib based on the exposure data will be produced separately. Percentage overall compliance will be summarized using the mean, standard deviation, minimum, median, and maximum. In addition, percentage overall compliance will be categorized and summarized by <80%, 80%-105%, and >105%.

The calculation of overall compliance is based on the entire interval of dosing for dabrafenib and trametinib. The formula for daily dose medication is compliance (%) =  $[\text{total cumulative actual dose} / (\text{duration of study treatment} * \text{prescribed dose})] * 100$  where duration of study treatment is last dose - first dose + 1.

A listing of overall compliance will be produced.

In addition, summaries of study treatment exposure and dose modifications (e.g., number of dose reductions, number of dose interruptions) will further characterize compliance. These analyses are described in Section [12.1](#) 'Extent of Exposure'.

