## 5.2. Dosage and Administration

### 5.2.1. Dabrafenib and Trametinib Combination

- Dabrafenib, 150 mg, BID;
- Trametinib, 2.0 mg, once daily.

When administered in combination with trametinib, take the once-daily dose of trametinib at approximately the same time each day with either the morning dose or the evening dose of dabrafenib. The second dose of dabrafenib (150 mg) should be administered approximately 12 hours after the morning dose. Study medication should be taken orally with approximately 200 mL of water under fasting conditions, either 1 hour before or 2 hours after a meal.

If a subject vomits after taking study medication, the subject should be instructed not to retake the dose and should take the next dose as originally scheduled.

If administration of trametinib is interrupted or permanently discontinued, administration of dabrafenib may be continued. If administration of dabrafenib is interrupted or permanently discontinued, administration of trametinib may continue.

If a subject misses a dose of dabrafenib, the subject may take the dose immediately if the next dose is scheduled for at least 6 hours later. If the next scheduled dose of dabrafenib is due in less than 6 hours, the subject should skip the dose and resume dabrafenib dosing at the next scheduled dose. If a subject misses a dose of trametinib, the subject may take the dose immediately if the next dose is scheduled for at least 12 hours later.

1. See Section [5.8](#) for dose modification guidelines on dabrafenib and trametinib.

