### 5.7. Treatment Compliance

Subjects will be instructed to return treatment bottles at each visit. Compliance with study treatment will be assessed by querying the subject and through pill count at each visit. Compliance will be documented in the source documents and the eCRF.

A record of the number of dabrafenib capsules and trametinib tablets dispensed to and taken by each subject must be maintained and reconciled with study treatment and compliance records. Treatment start and stop dates, including dates of dose modifications and/or interruptions will also be recorded in the eCRF. The investigator will make every effort to bring non-compliant subjects into compliance.

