### **9.2.6. Imputation of Missing Exposure End Dates**

The rules for imputing missing exposure end dates given in this section apply to both dabrafenib and trametinib. The study treatment end date variable will hold the last date of exposure for either dabrafenib or trametinib, that is, the latest exposure end date across all study treatments.

In general, completely missing dates are not imputed. However, subjects in oncology trials may still be on study treatment when analyses are performed and so may have missing exposure end dates in their last dosing record. Missing exposure end dates for subjects who are still on study treatment at the time of an analysis will be imputed. For subjects with missing exposure end dates at the time of data cutoff, the exposure end date will be imputed to the earliest of: the date of the data cutoff, the date of withdrawal from the study, or the death date. The imputed exposure end date will be used to calculate cumulative dose and exposure duration. The imputed exposure end date will be stored in the exposure analysis dataset and an exposure end date imputation flag variable will be derived indicating which exposure end date records are imputed. Imputed exposure end dates will also be stored on the study treatment end date variable.

For subjects who have missing end dates in their last exposure record because they are still on study treatment, the on-therapy indicator variables (time in relation to study treatment) are assigned to on-therapy for all records where the 'dataset'.date' is after or on the study treatment start date.

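### The SAP 10.4 compliance formula counts protocol-directed hold days against the subject and leaves the prescribed dose and the dosing interval undefined

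*SAP*

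**What the plan says.** SAP 10.4 defines overall compliance, as a percentage, as the "total cumulative actual dose" divided by the product of duration of study treatment and prescribed dose, "where duration of study treatment is last dose - first dose + 1". It adds: "The calculation of overall compliance is based on the entire interval of dosing for dabrafenib and trametinib". The result is summarised separately for dabrafenib and trametinib (Tables 1.6010 and 1.6011), with descriptive statistics and three bands: below 80%, 80% to 105%, and above 105%. The section does not say whether the prescribed dose is the starting dose or the dose in force on the day. Nor does it say whether first and last dose are those of the drug being summarised.

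SAP 9.2.6 defines a shared end date: "The study treatment end date variable will hold the last date of exposure for either dabrafenib or trametinib".

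The protocol directs departures from full dosing. Table 11 interrupts dabrafenib at first, second and subsequent pyrexia events. Table 5 interrupts treatment for intolerable grade 2 toxicity and above, with restart at a lower level. Section 5.2.1 allows the drugs to be separated: "If administration of trametinib is interrupted or permanently discontinued, administration of dabrafenib may be continued". Section 4.2.1 treats a subject who stops one drug and stays on the other as still on study treatment. On measurement, section 5.7 says: "Compliance with study treatment will be assessed by querying the subject and through pill count at each visit".

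**The concern.** A compliance percentage should show whether subjects took what they were told to take. Here a day without drug on the investigator's instruction counts the same as a day the subject forgot. A low figure could mean toxicity management, missed doses or both, and the table cannot separate them.

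The ratio is in substance a dose-intensity measure. SAP 12.1 already defines average daily dose as cumulative dose over duration of exposure. Over the same interval, the 10.4 ratio is that average divided by the prescribed dose. Protocol 9.3.5.2.1 puts dose intensity under extent of exposure, while protocol 5.7 treats compliance as a separate matter assessed by questioning and pill count.

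The undefined terms add a second problem: two programmers working from the same text could produce materially different tables.

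**Working it through.** Neither document states a compliance result, so there is no figure to reproduce. The check applies the SAP formula to hypothetical subjects who take every dose they are instructed to take.

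Inputs:
- Formula and duration: SAP 10.4.
- Starting doses: dabrafenib 150 mg twice daily, which is 300 mg/day, and trametinib 2 mg/day (SAP 3).
- Reduced levels: dabrafenib 100 mg or 75 mg twice daily, trametinib 1.5 mg or 1.0 mg once daily (Protocol Table 4).
- Treatment lengths and event days: assumed for illustration. The documents give no share of time on hold.

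**1. Directed holds.** At constant dose, with h hold days inside an interval of T days, score = (T − h)/T. This is below 100% for any h > 0, and below 80% when h/T > 0.20.

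| Hold (days) | Interval (days) | Score |
|---|---|---|
| 14 | 56 | 42/56 = 75.0% |
| 14 | 84 | 70/84 = 83.3% |
| 21 | 84 | 63/84 = 75.0% |
| 14 | 168 | 154/168 = 91.7% |
| 42 | 168 | 126/168 = 75.0% |

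A subject who misses 21 of 84 days without any instruction also scores 75.0%, so the formula cannot tell the two apart.

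**2. Which prescribed dose.** Take dabrafenib at 300 mg/day for 60 days, a 7-day directed hold, then 200 mg/day for 101 days, 168 days in all.
- Dose taken: 300×60 + 200×101 = 38,200 mg.
- Starting dose in the denominator: 300×168 = 50,400 mg; 38,200/50,400 = 75.8%.
- Current dose in the denominator, counted in days: 161/168 = 95.8%. In milligrams, charging hold days at 300 mg gives 38,200/40,300 = 94.8%, and charging them at 200 mg gives 38,200/39,600 = 96.5%.
- True adherence: 100%.

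Under the starting-dose reading and without any hold, a subject at a fraction r of the starting dose for a share f of the interval falls below 80% when f(1 − r) > 0.20. That means more than 60% of the time at dabrafenib 100 mg twice daily, 40% at 75 mg twice daily, 80% at trametinib 1.5 mg, or 40% at 1.0 mg.

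**3. Which interval.** Trametinib is stopped as directed at day 84 and dabrafenib continues to day 336. On trametinib's own dates the score is 84/84 = 100%. On the shared end date it is 84/336 = 25%.

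**4. With the dose prescribed on each day as denominator.** For the subject in step 2: 38,200/(300×60 + 0×7 + 200×101) = 38,200/38,200 = 100%. The subject who skipped 21 of 84 days without instruction still scores 75%.

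**The case against.** The best defence is that little depends on this table and that the SAP surrounds it with better information. Section 10.4 also asks for a drug accountability listing of dispensed and returned product, and says that exposure and dose-modification summaries complete the picture. Section 12.1 summarises reductions and interruptions by drug, with reasons, and gives the duration of interruptions. That is true, but none of it corrects the percentage itself, and accountability is only listed.

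The examples can also be made milder. A 7-day hold in 168 days with no reduction scores 95.8%. If the step 2 subject is re-escalated after 28 days, the score on the starting-dose reading is (300×60 + 200×28 + 300×73)/50,400 = 45,500/50,400 = 90.3%. This stands: short holds and brief reductions leave a subject in the middle band.

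Several stronger readings are tempting and are not supported:
- That adherent subjects are classed as non-compliant. No band carries that label and none triggers any action.
- That reductions certainly lower the score. This needs the starting dose. A single multiplier suggests it, but the text does not say so.
- That a single-drug stop certainly lowers the score. The drugs are summarised separately, 10.4 gives its own definition of duration, and it does not cite 9.2.6.
- That twice-daily dabrafenib scores double, because 150 mg would be entered. The formula is stated for daily dosing, and 150 mg twice daily is 300 mg per day. This would be a programming mistake, not something the plan directs.
- That the pyrexia rates of 52% and 58% quoted in protocol section 1.1.3.2 show how often the score is distorted. They are incidences from another study, not time on hold.

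**Conclusion.** The treatment of hold days is a definite fault. Under either reading of prescribed dose and either reading of the interval, a directed hold followed by restart pulls a fully adherent subject below 100%. At constant dose the subject enters the lowest band once holds pass 20% of the interval. The reduction effect (75.8% against about 96%) and the single-drug-stop effect (25% against 100%) are ambiguities whose size depends on how the text is programmed. All of these figures rest on assumed treatment histories; how many subjects would be affected cannot be judged from the documents.

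The consequence is limited to the two descriptive compliance tables and their listings. Efficacy and safety analyses use all treated subjects (SAP 6.4), and no population, endpoint or decision rule refers to compliance, so the primary test is untouched. A reader could, however, take a low compliance figure as poor adherence when it reflects directed dose management.

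**What to change.** Redefine compliance in SAP 10.4, separately for each drug, as 100 × cumulative dose taken ÷ sum of the total daily dose prescribed on each day from that drug's own first dose to its own last dose. Count 0 on investigator-directed hold days, the reduced level after a directed reduction, and both daily doses for dabrafenib. Days missed without instruction stay in the denominator at the dose then prescribed.

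If the present ratio is kept, call it relative dose intensity, state that its denominator is the starting daily dose, state which interval it uses, and report it with the exposure summaries of SAP 12.1.

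The cost is a few lines of SAP text and minor programming. Protocol 5.7 already has dates of dose modifications and interruptions recorded in the eCRF, and SAP 12.1 already uses the reasons for them, which is what separates a directed hold from a missed dose.

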#### **10.5. Concomitant Medications**

[figure not shown]
Concomitant medications will be coded using WHODrug coding dictionary, summarized, and listed. The summary of concomitant medications will show the number and percentage of subjects taking concomitant medications by Ingredient. Multi-ingredient products will be summarized by their separate ingredients rather than as a combination of ingredients. Anatomical Therapeutic Chemical (ATC) classification Level 1 (Body System) information will be included in the dataset created but will not appear on the listing or summary.

In the summary of concomitant medications, each subject is counted once within each unique ingredient. For example, if a subject takes Amoxicillin on two separate occasions, the subject is counted only once under the ingredient “Amoxicillin”.

In the summary of concomitant medications, the ingredients will be summarized by the base only, using CMBASECD and CMBASE.

A separate listing of prior and concomitant medications of subjects with diabetes at baseline (as reporting on the medical history page of the eCRF) will be produced.

Blood products or blood supportive care products with onset date within the on-therapy window will be included in the summary tables. The frequency and percentage of subjects using blood products and blood supportive care products after the start of study medication will be provided. Supporting listings will also be provided.

## **11. EFFICACY**

All efficacy analyses will be based on the ATS population as defined in Section 6 unless otherwise specified. All analyses will be presented by cohort.

Efficacy assessments are based on modified RECIST 1.1. Primary assessments will be based on imaging data. Investigator assessments will be considered as primary assessments. Independent Reviewer assessments, will be supplementary.

Note: If needed, the IRC charter will have further modifications to RECIST 1.1 because of additional instructions needed for the independent review. Specifically, instructions will be provided with respect to ascites, pleural effusion, and subjects with no lesions documented at baseline.

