**7.3.2.3. Extracranial Response (ER) - Evaluation of Extracranial Target Lesions**

Definitions for assessment of response for *extracranial target* lesion(s) are as follows:

- Complete Response (CR): Disappearance of all target lesions.
- Partial Response (PR): At least a 30% decrease in the sum of the diameters of target lesions, taking as a reference, the baseline sum of the diameters (e.g. percent change from baseline).
- Stable Disease (SD): Neither sufficient shrinkage to qualify for PR nor sufficient increase to qualify for progressive disease.
- Progressive Disease (PD): At least a 20% increase in the sum of the diameters of target lesions, taking as a reference, the smallest sum of diameters recorded since the treatment started (e.g. percent change from nadir, where nadir is defined as the smallest sum of diameters recorded since treatment start). In addition, the sum must

have an absolute increase from nadir of 5mm.

- Not Evaluable (NE): Cannot be classified by one of the four preceding definitions.

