**7.3.2.4. Extracranial Response (ER) - Evaluation of Extracranial Non-Target Lesions**

Definitions for assessment of response for extracranial non-target lesions are as follows:

- Complete Response (CR): The disappearance of all non-target lesions.
- Non-CR/Non-PD: The persistence of 1 or more non-target lesion(s) identified as a site of disease.
- Progressive Disease (PD): Unequivocal progression of existing non-target lesions.
- Not Applicable (NA): No extracranial non-target lesions at baseline.
- Not Evaluable (NE): Cannot be classified by one of the four preceding definitions.

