## **6. ANALYSIS POPULATIONS**

### **6.1. All Treated Populations**

All subjects who receive at least one dose of study medication will comprise the All Treated subjects (ATS) population.

The V600E population will comprise all BRAF V600E mutation positive subjects in the ATS population.

The V600D/K/R population will comprise all BRAF V600D/K/R mutation positive subjects in the ATS population.

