#### **9.2.12. Date Associated with Response**

For each disease assessment after baseline, determine the dates associated with intracranial, extracranial, and overall response. For any type of complete response (CR) or partial response (PR), assign to the latest date within the disease assessments. For any type of stable disease (SD), Non-CR/Non-PD or Not Evaluable, assign to the earliest date within the disease assessments. For any type of progressive disease (PD), assign to the earliest assessment date associated with the progression.

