## 11.2. Secondary Efficacy Analyses

Intracranial Response (IR) in Cohorts B, C, and D

Intracranial response will be summarized for Cohorts B, C, and D as for Cohort A.

Extracranial Response (ER) in Cohorts A, B, C, and D

The extracranial response rate (ERR) is defined as the percentage of subjects achieving a confirmed extracranial CR or PR from the start of treatment until disease progression or the start of new anti-cancer therapy. This will be based on investigator-assessed best extracranial response.

Stable extracranial disease requires meeting the SD criteria at least once after the first dose of study treatment at a minimum interval of 8 weeks. To be assigned a status of extracranial PR or CR, a confirmatory disease assessment for extracranial disease should be performed not less than 4 weeks after the criteria for response are first met.

The Independent Reviewer-assessed best extracranial response will also be summarized.

Subjects with Not Evaluable (NE) or missing extracranial response will be treated as non-responders; i.e., they will be included in the denominator when calculating the percentage.

The exact 95% CI for the extracranial response rate will be calculated.

All data relating to extracranial response from the investigator and, if done, the independent reviewer will be listed, including lesion measurements, response assessments and best response.

A plot of the maximum percent tumor reduction in extracranial target lesions from baseline will be provided. The plot will be color-coded for best extracranial response. The subject number will be indicated on the plot.

Extracranial response will be determined using only extracranial target, non-target, and new lesions, using the criteria specified in the protocol.

Target Lesions	Non-Target Lesions	New Lesions	Extracranial Response
CR	CR or NA	No	CR
CR	Non-CR/Non-PD or NE	No	PR
PR	Non-PD or NA or NE	No	PR
SD	Non-PD or NA or NE	No	SD
NE	Non-PD or NA or NE	No	NE
PD	Any	Yes or No	PD
Any	PD	Yes or No	PD
Any	Any	Yes	PD

CR=complete response, PR = partial response, SD=stable disease, PD=progressive disease, NA= Not applicable, and NE=Not Evaluable

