#### Intracranial, Extracranial, and Overall Disease Control in Cohorts A, B, C, and D

The intracranial disease control (IDC), extracranial disease control (EDC), and overall disease control (ODC) are defined as CR+PR+SD for intracranial, extracranial, and overall disease control, respectively. Disease control rates are defined as the percentage of subjects achieving a confirmed overall CR or PR, or SD for at least 8 weeks from the start of study treatment, from the start of treatment until disease progression or the start of new anti-cancer therapy. This will be based on investigator-assessed responses.

The Independent Reviewer-assessed disease control rate will also be summarized.

Subjects with Not Evaluable (NE) or missing intracranial, extracranial, or overall response will be treated as non-responders; i.e., they will be included in the denominator when calculating the percentage.

Exact 95% CIs for the disease control rates will be calculated.

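### ERR and EDC default to all treated subjects, but the SAP's extracranial table gives no route to response without an extracranial target lesion

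*SAP*

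**What the plan says.** SAP Section 11 sets the default: "All efficacy analyses will be based on the ATS population as defined in Section 6 unless otherwise specified". Section 6.1 defines that population by dosing alone: "All subjects who receive at least one dose of study medication will comprise the All Treated subjects (ATS) population".

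Section 11.2 then gives the two endpoints without naming a subset. For response, "The extracranial response rate (ERR) is defined as the percentage of subjects achieving a confirmed extracranial CR or PR", and "Subjects with Not Evaluable (NE) or missing extracranial response will be treated as non-responders", so they remain in the denominator. For disease control, "Disease control rates are defined as the percentage of subjects achieving a confirmed overall CR or PR, or SD" lasting at least 8 weeks, with the same treatment of NE and missing responses. The response table in 11.2 combines target, non-target and new extracranial lesions. Its target column holds CR, PR, SD, NE, PD or any status; a not-applicable entry appears only for non-target lesions.

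Protocol Section 7.3.2.9 introduces its own time-point table for subjects with measurable extracranial disease at baseline. Protocol Table 1, which defines the endpoint, expresses it as a percentage of subjects and does not say which ones.

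**The concern.** ERR and EDC are secondary endpoints in all four cohorts and will be read as measures of activity outside the brain. The trial enrols on intracranial disease. A subject with no extracranial disease cannot have an extracranial response, yet the default counts that subject in the denominator. This differs from counting a subject who has disease but no usable scan as a non-responder, which is a conservative convention about missing information. Here there is nothing to assess, and the reported rate falls as more such subjects enrol, whatever the drugs do.

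The SAP shows some awareness of the issue. A note in Section 11 says the independent review charter, if needed, will give instructions for subjects with no lesions documented at baseline. No matching rule covers the investigator assessment, which is primary.

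**Working it through.** **Can such subjects be enrolled?** Protocol 4.1.2, criterion 6, asks for at least one measurable intracranial lesion. Section 7.3.1 says that having only non-measurable intracranial lesions excludes a subject; the parallel extracranial definition in 7.3.1.1 carries no exclusion. Section 7.3.2.5 provides a not-applicable category, under overall response, for subjects without extracranial target lesions at baseline. Part of criterion 4 and all of criterion 11 are not visible, so this holds for the visible criteria.

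**How would the SAP count them?** Take a subject with no extracranial disease. There are three possible codings:

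- *NE.* Protocol 7.3.2.3 has no not-applicable category for extracranial target lesions, only the catch-all "Not Evaluable (NE): Cannot be classified by one of the four preceding definitions". SAP 11.2 then makes the subject a non-responder.
- *Missing.* The same rule applies.
- *Not applicable.* SAP 9.1 says such answers are not missing data, so the NE/missing rule does not name the subject. The all-treated default still keeps the subject in the denominator, and no table row gives a response.

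Each coding adds 1 to the denominator and 0 to the numerator. A new lesion could make the subject PD, but nothing leads to CR, PR or SD.

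For a subject with only non-measurable extracranial disease the outcome is open. Protocol 7.3.2.4 defines a non-target response, "Complete Response (CR): The disappearance of all non-target lesions", and SAP 9.2.12 recognises a further status when assigning dates: "For any type of stable disease (SD), Non-CR/Non-PD or Not Evaluable, assign to the earliest date within the disease assessments". The SAP table does not say how either counts when there is no target lesion.

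**Formula.** The documents give no expected ERR or EDC and no f, so there is no planned figure to reproduce. Let n be treated subjects, m those with measurable extracranial disease, f = 1 − m/n, r the rate among the m, and c the number outside that set who are credited. Then

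all-treated rate = (r·m + c)/n = r(1 − f) + c/n.

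**No credit (c = 0), Cohort A, n = 75.** Assumed: r = 50% for ERR, r = 80% for EDC, and f. Intervals are exact 95%.

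| Endpoint | f | Measurable-disease denominator | All-treated denominator |
|---|---|---|---|
| ERR | 7/75 = 9.3% | 34/68 = 50.0% (37.6–62.4) | 34/75 = 45.3% (33.8–57.3) |
| ERR | 15/75 = 20.0% | 30/60 = 50.0% (36.8–63.2) | 30/75 = 40.0% (28.9–52.0) |
| ERR | 23/75 = 30.7% | 26/52 = 50.0% (35.8–64.2) | 26/75 = 34.7% (24.0–46.5) |
| EDC | 15/75 = 20.0% | 48/60 = 80.0% (67.7–89.2) | 48/75 = 64.0% (52.1–74.8) |

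As a check on the assumed rates, borrow the overall (not extracranial) results that protocol 1.1.3.2 reports for the earlier combination study: 56% response and (4 + 39 + 29)/77 = 93.5% disease control. At f = 20%, ERR is 34/60 = 56.7% against 34/75 = 45.3%, and EDC is 56/60 = 93.3% against 56/75 = 74.7%. At f near 5% (71 of 75 measurable), ERR is 40/71 = 56.3% against 40/75 = 53.3%, and EDC is 66/71 = 93.0% against 66/75 = 88.0%.

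**With credit (c > 0), f = 20%.** The two denominators agree when c = r·f·n, that is 0.5 × 15 = 7.5 subjects for ERR and 0.8 × 15 = 12 for EDC. Crediting 8 of the 15 gives ERR (30 + 8)/75 = 50.7%, just above the subset rate. Crediting 12 gives EDC (48 + 12)/75 = 80.0%, and crediting all 15 gives 63/75 = 84.0%. Only subjects with non-measurable-only disease could be credited, so c cannot exceed their number, which is also not given.

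**The case against.** The strongest reply is that nothing is in conflict. A reader might infer that the protocol restricts ERR to measurable extracranial disease and the SAP departs from it. The documents do not support that: Section 7.3.2.9 scopes only the time-point table, the endpoint in Table 1 carries no restriction, and the SAP follows Table 1. The scoping sentence also refers to Section 7.3.1, which holds the intracranial definitions, so it is weak evidence of an intended denominator. This objection stands. What remains is an all-treated default that does not fit the table used to assign responses.

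A reader might also infer that every subject without measurable extracranial disease is a non-responder, so both rates must fall. That is sound for subjects with no extracranial disease. It is not established for non-measurable-only disease, where the counting rule is missing and the direction depends on how many are credited.

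Other points carry some weight. All-treated denominators are common and usually conservative. The dataset specifications and display shells are separate documents that were not available and may handle not-applicable rows. Display 1.2110 summarises baseline extracranial burden by cohort, and the lesion and response listings would let a reader rebuild subset rates. The share f may be small. These limit how large the problem is likely to be; they do not put a denominator rule into the SAP.

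**Conclusion.** The point holds in this form: as written, the SAP counts treated subjects with no extracranial disease in ERR and EDC with no route to response, and it does not say how non-measurable-only disease counts. The first lowers both rates as measures of extracranial activity whenever such subjects are enrolled. The net direction over all subjects without measurable disease is certain only if none is credited, in which case the relative loss equals f.

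The size is unknown because f is not in the documents. The 10-point ERR and 16-point EDC differences at f = 20% are illustrations that rest on assumed rates and no credit; they are not estimates or bounds. The endpoints are descriptive, and both documents rule out statistical comparison of the cohorts. The primary test, its type I error and power, and the intracranial and overall response rates are unaffected. Correcting this is worthwhile, but it does not threaten the trial's main conclusion.

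**What to change.** In SAP 11.2:

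- Report ERR and EDC with exact confidence intervals among ATS subjects with measurable extracranial disease at baseline, and print that n for each cohort.
- Within that set, keep NE and missing responses as non-responders.
- Show subjects with no extracranial disease and subjects with non-measurable-only disease in separate rows, including any non-target CR, new lesion or progression.
- Keep the all-treated rate alongside, and record when the change was made.

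The work is one paragraph and a flag derived from baseline lesion data already collected.

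There are two costs. First, the ERR interval widens: in the f = 20% example, from 23.1 to 26.4 points. Second, the SAP is dated 05-Mar-2018, the study is open-label, and the revision history records that independent review had been done. A change that moves the rates upward (when no one outside the subset is credited) could look data-driven. Dating the change and printing both denominators makes that visible to the reader.
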